11.4 Efficacy Parameters

11.4.1 Co-primary Efficacy Endpoints

There will be two co-primary efficacy endpoints for this study. The first co-primary efficacy endpoint will be the absolute CFB in inflammatory lesion counts at Week 12. This variable will be considered a continuous variable.

The second co-primary efficacy endpoint will be IGA success at Week 12. IGA success will be a dichotomous variable defined as at least 2-point decrease from baseline on the IGA assessment as well as a score of clear (0) or almost clear (1) on the IGA assessment.

11.4.2 Secondary Efficacy Endpoints

There will be **four** secondary efficacy endpoints for this study, percent CFB in inflammatory lesion counts at Week 12, **and absolute and percent CFB in inflammatory lesion counts at Weeks 9, 6, and 3**. These variables will be considered continuous variables.

11.4.3 Missing Data Handling for Co-Primary and Secondary Endpoints

For the co-primary and secondary efficacy analyses, the primary missing data imputation method is multiple imputation (MI), as outlined in the following procedures:

- The SAS PROC MI procedure with a fully conditional specifications (FCS) method will be used to create 20 imputations. The FCS is proposed as it allows for accommodation of categorical variables and it has the versatility to handle arbitrary missing data patterns. Based on these 20 imputations, the relative efficiency will be 0.995 for 10% of missing data and 0.990 for 20% of missing data (Rubin, 1976, 1987, 1996).
- For inflammatory lesion counts, if any of the subtypes (papules, pustules, and nodules/cysts) is missing, the inflammatory lesion count is missing. The variables included in the imputations are age, sex, and the raw measurements of the corresponding endpoint counts at baseline, Week 3, Week 6, Week 9, and Week 12
- For IGA, the raw scores will be used for the imputation. The variables included in the imputations are age, sex, and the measurements of the endpoint at baseline, Week 3, Week 6, Week 9, and Week 12
- All imputations will be performed by treatment group based on the randomized study medication. The number of imputations is set at 20 with number of 50 burn-in iterations. The seed used for imputation for all endpoints is █. For IGA raw scores and lesion counts, regression with predictive mean matching method will be used. The imputed values will be rounded to the nearest integer.
- An analysis of covariance (ANCOVA) model for continuous endpoints (inflammatory lesion counts) will be performed for each of the imputed datasets.
- A Cochran-Mantel-Haenszel (CMH) analysis for the binary endpoint (IGA success) will be performed for each of the imputed datasets.
- The SAS PROC MIANALYZE procedure will be used to produce final parameter estimates, including the point estimates and standard errors, adjusted treatment differences, confidence intervals and p-values for the primary and secondary variables.
- For the CMH test, the Wilson-Hilferty transformation (Wilson & Hilferty, 1931, O'Kelly & Ratitch, 2014) will be used. Under the null hypothesis, the transformed statistic is approximately normally distributed:

$$wh_CMH^{(m)} = \sqrt{\frac{cmh^{(m)}}{k}} \sim normal(1 - \frac{2}{9k}, \frac{2}{9k})$$

Where $cmh^{(m)}$ is the chi-square statistics each with k degrees of freedom from $m = 1, \dots, M$ imputed datasets. In this case, $k=1$. This statistic will be passed to PROC MIANALYZE to obtain the combined p-value for CMH test.

The same method will be used to obtain the p-values from the Breslow-Day test.

11.4.4 Other Efficacy Endpoints

11.5 Analysis of Efficacy Variables

11.5.1 CFB in Inflammatory Lesion Counts

The co-primary endpoint, absolute CFB in inflammatory lesion counts at Week 12, will be analyzed using an analysis of covariance (ANCOVA) model with the baseline value as a covariate and additional terms included to represent effects of treatment and (pooled) site. The primary efficacy analysis will be based on the ITT population. **Missing data will be imputed using the MI approach described in Section 11.4.3.** The adjusted means with associated 95% CIs from the ANCOVA model will also be presented for each treatment and for the difference between the treatments **at Week 12**. Statistical significance between the treatments, sarecycline compared to placebo, will be declared if the p-value of the hypothesis test from the ANCOVA model is less than or equal to 0.05. The ANCOVA model will be performed using SAS® PROC MIXED with the methodology of Littell et al. (1996).

Let X_{ijk} and Y_{ijk} be the baseline and endpoint values for the k th subject in the j th site and the i th treatment, where $k=1, \dots, n_j$, $j=1, \dots, c$ (the number of sites after pooling, if applicable) and $i=sarecycline, placebo$. Then

$$Y_{ijk} - X_{ijk} = \mu + \tau_i + \gamma_j + \beta X_{ijk} + \varepsilon_{ijk} \quad (1)$$

where μ is the overall mean, τ is the fixed effect of the i th treatment, γ is the fixed effect of the j th site, β is a regression coefficient for baseline and ε_{ijk} is the $NID(0, \sigma^2)$ random error component. Hypothesis tests for the active treatment effect of sarecycline compared to placebo will be conducted using differences of adjusted means.

Residuals will be evaluated using SAS® PROC UNIVARIATE. The assumption of a random error component $\sim NID(0, \sigma^2)$ will be tested by examining skewness and kurtosis following D'Agostino et al. (1990) with the residuals pooled over both treatments. Additionally, homogeneity of variances across treatment groups will be examined using Levene's Test (Glaser 1982) with significance level of 0.05, based on absolute values of the residuals from the residual medians for each treatment. The data will be determined non-normal if the p-value for either the D'Agostino Skewness Test or D'Agostino Kurtosis Test is less than 0.05. **Because of the multiple datasets created by using the MI approach, the**

p-value used for each of these tests will be the median p-value after the analysis has been performed on each dataset. If the data do not meet the normality or homogeneity assumptions of the parametric analyses, then a rank transformation will be applied to the raw data and the primary analysis will proceed using an ANCOVA model on the ranks with the baseline value as a covariate and effects of treatment and (pooled) site. Tied values will receive the mean value (midranks) of the corresponding ranks.

As site is included in the **primary** ANCOVA model, a treatment-by-site interaction will be investigated as an exploratory analysis to assess the homogeneity of treatment effects across site. This effect will be investigated analytically prior to any pooling of sites by adding the interaction term to the ANCOVA model and testing for significance. Because interactions are not powered in this study, testing for significance will be at the 0.10 level. However, any significant interaction findings at the 0.10 level will also take into account the potential for spurious results. Further exploration may be done graphically with interaction plots to determine the nature of the interaction and to identify any “outlier” sites with attention focused on qualitative differences in treatment effects. If large differences in treatment effects are seen in any “extreme” sites, then sensitivity analyses will be performed that exclude sites with the highest extreme treatment effect values from the analysis. Any such sites may be further investigated for explanation involving study conduct, subject demographics, current medications, etc.

11.5.2 IGA Success

The co-primary efficacy endpoint, percentage of subjects of IGA success at Week 12, will be analyzed for the ITT population using the Cochran-Mantel-Haenszel (CMH) test with adjustment for (pooled) site. **Missing data will be imputed using the MI approach described in Section 11.4.3.** The **rate** difference and the 95% CIs for the **rate** difference and the relative **rate** and the 95% CIs for the relative **rate** will be presented as well. **The CIs for the treatment rate difference will be based on two-sided 95% Wald type CIs with CMH weights (Kim & Won, 2013, Yan & Su, 2012).**

The homogeneity of treatment effects across (pooled) site will be investigated as an exploratory analysis using the Breslow-Day test. If the Breslow-Day test indicates large heterogeneity in the odds ratios across (pooled) site, then further exploration may be done graphically or with further investigation for explanation involving study conduct, subject demographics, current medications, etc.

11.5.3 Secondary Endpoint Analyses

A hierarchical testing approach will be used for the secondary efficacy endpoints, percent CFB in inflammatory lesion counts at Week 12, **and absolute and percent CFB in inflammatory lesion counts at Weeks 9, 6, and 3 (using ANCOVA), such that statistical testing will only be performed if both co-primary efficacy endpoints are statistically superior to placebo at $\alpha=0.05$.** **In addition, statistical testing of the secondary endpoints will be conducted in the following order, with all tests proceeding at the 0.05 level if and only if the previous tests were all significant at the 0.05 level:**

- 1. Percent CFB for inflammatory lesion counts at Week 12 (must be significant at the 0.05 level to proceed to the next analyses)**
- 2. Absolute and percent CFB for inflammatory lesion counts at Week 9 (both endpoints must be significant at the 0.05 level to proceed to the next analyses)**
- 3. Absolute and percent CFB for inflammatory lesion counts at Week 6 (both endpoints must be significant at the 0.05 level to proceed to the next analyses)**
- 4. Absolute and percent CFB for inflammatory lesion counts at Week 3 (both endpoints must meet the 0.05 level for Week 3 to meet statistical significance)**

These secondary endpoints will all be analyzed using an analysis of covariance (ANCOVA) model with terms included to represent effects of treatment and (pooled) site and the baseline values as a covariate for the ITT population. **Missing data for the co-primary and secondary endpoints will be imputed using an MI approach, as described in Section 11.4.3.** The adjusted means with associated 95% CIs for the ANCOVA model will also be presented for each treatment and for the difference between the treatments. Statistical significance between the treatments, sarecycline compared to placebo, will be declared if the p-value of the hypothesis test from the ANCOVA model is less than or equal to 0.05. **For percent CFB at Week 12, formal procedures for testing assumptions of the ANCOVA model (and alternative procedures when assumptions are unmet, e.g., nonparametric analysis) will be specified in the SAP. The percent CFB analysis for Weeks 9, 6, and 3 will use the same methods as determined by the Week 12 analysis (i.e., based on the values or on the ranks). In addition, the absolute CFB analysis for Weeks 9, 6, and 3 will use the same methods as determined by the co-primary CFB Week 12 analysis for inflammatory lesion counts (i.e., based on the values or on the ranks).**

For the Week 12 percent CFB analysis, as site is included in the ANCOVA model, a treatment-by-site interaction will be investigated as an exploratory analysis to assess the homogeneity of treatment effects across site. This effect will be investigated analytically by adding the interaction term to the ANCOVA model and testing for significance. Because interactions are not powered in this study, testing for significance will be at the 0.10 level. However, any significant interaction findings at the 0.10 level will also take into account the potential for spurious results with attention focused on qualitative differences in treatment effects. If large differences in treatment effects are seen in any “extreme” sites, then sensitivity analyses will be performed that exclude sites with the highest extreme treatment effect values from the analysis. Further exploration may be done graphically with interaction plots to determine the nature of the interaction and to identify any “outlier” sites. Any such sites may be further investigated for explanation involving study conduct, subject demographics, current medications, etc.

11.5.4 [REDACTED]

[REDACTED]

[REDACTED]

11.5.5 Additional Analyses

Efficacy data will be analyzed for each OC visit.

11.5.6 Sensitivity Analyses

Sensitivity analyses will investigate the impact of missing data on the robustness of the results. Reasons for missing data and time to drop-out will be explored in a descriptive fashion for each treatment. Efficacy responses through time for each treatment will be investigated for each treatment for subjects that completed the study versus for those subjects that discontinued the study. Additionally, logistic regression models may be used to explore efficacy responses for subjects who completed the study compared to those subjects who dropped out. Finally, the following sensitivity analyses of the co-primary efficacy endpoint data will be provided to explore the impact of missing data on the robustness of the results. Additional sensitivity analyses may be described in the Statistical Analysis Plan prior to database lock.

Sensitivity Analyses for Continuous Variables

- Efficacy data will be summarized and analyzed **according to an ANCOVA model with the baseline value as a covariate and effects of treatment and (pooled) site** using the **per-protocol (PP) population with OC data**.
- **LOCF will be used as an imputation method for cases where the Week 12 CFB in inflammatory lesion counts value is missing. The endpoint will then be analyzed according to an ANCOVA model with the baseline value as a covariate and effects of treatment and (pooled) site.**
- Baseline observation carried forward will be used as an imputation method for cases where the Week 12 CFB in inflammatory lesion counts value is missing. The endpoint will then be analyzed according to the **ANCOVA model with the baseline value as a covariate and effects of treatment and (pooled) site**.
- Mixed model repeated measures (MMRM) analysis will be used to explore the sensitivity of data handling for CFB in inflammatory lesion counts for subjects who withdraw from the study. The model will include the fixed effects of treatment, pooled site, and visit, the baseline value as the covariate, and the treatment-by-visit interaction term. An unstructured covariance matrix will be used initially in the model for the correlation pattern among the repeated measures. If this does not converge, then the Toeplitz covariance structure (TYPE=TOEP in SAS MIXED procedure) will be used instead. If the results from the MMRM analyses differ qualitatively with the results from the

primary efficacy analysis, further analyses will be performed to investigate the causes of the difference. However, the results from the primary efficacy analysis will be considered the primary efficacy results.

Sensitivity Analyses for Categorical Variables

- Efficacy data will be summarized and analyzed using **the CMH test with adjustment for (pooled) site using the PP population with OC data**.
- For IGA success, subjects who discontinue from the study early will be coded as failures **for the Week 12 analysis**. A sensitivity analysis of IGA success using this data handling convention will be performed using the **CMH test with adjustment for (pooled) site on the ITT population**.
- For IGA success, subjects who discontinue from the study early will be coded as failures for subjects on sarecycline and successes for subjects on placebo **for the Week 12 analysis**. A sensitivity analysis of IGA success using this data handling convention will be performed using the **CMH test with adjustment for (pooled) site on the ITT population**.

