2 SYNOPSIS

Warner Chilcott (US), LLC, US Regulatory Agent of Warner Chilcott Company, LLC, an Allergan Affiliate
Name of Finished Product: Sarecycline tablets
Study Title: A Randomized, Multicenter, Double-blind, Placebo-controlled Study to Evaluate the Efficacy and Safety of 1.5 mg/kg per Day of Sarecycline Compared to Placebo in the Treatment of Acne Vulgaris
Study Number: SC1401
Study Phase: 3
Primary Objective: The primary objective is to evaluate the efficacy of oral sarecycline 1.5 mg/kg/day compared to placebo in treating inflammatory acne lesions in subjects with moderate to severe facial acne vulgaris based on Investigator's Global Assessment (IGA) score and inflammatory lesion counts.
Secondary Objectives: The secondary objectives are to evaluate the safety of oral sarecycline 1.5 mg/kg/day based on adverse events, vital signs, electrocardiograms, physical examinations and clinical laboratory tests.
Study Design: Randomized, double-blind, placebo-controlled, parallel group
Study Population: Males and females, 9 to 45 years of age (inclusive) with moderate to severe facial acne vulgaris
Number of Subjects: Approximately 1000 subjects enrolled at approximately 50 sites
Study drug; Dose; and Mode of Administration: Sarecycline tablets; 60 mg, 100 mg and 150 mg, providing a dose of 1.5 mg/kg/day; oral
Reference Therapy; Dose; and Mode of Administration: Matching placebo tablets; oral
Duration of Treatment: 12 weeks
Efficacy Assessments: IGA scores and lesion counts at baseline and following 3, 6, 9, and 12 weeks of treatment.

The co-primary efficacy endpoints will be the change from baseline (CFB) in inflammatory facial lesion counts at Week 12 and IGA success at Week 12.

Safety Assessments:

Adverse events, vital signs, electrocardiograms, physical examinations and clinical laboratory tests.

Pharmacokinetic Assessments:

Subjects will have the ability to participate in one of two PK sampling options: PK Schedule 1 or PK Schedule 2 (see below). **Additionally, subjects who are 9 to 11 years of age have the ability to participate in PK Schedule 3 (see below).** Subjects that do not participate in PK sampling are still eligible for study participation. For some of the sites, the only choices will be PK Schedule 2 or no PK sampling.

PK Schedule 1

Visit	Sample Time

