11.1 Determination of Sample Size

The sample size was selected to provide an adequate number of subjects to compare the efficacy of sarecycline treatment to placebo and to provide an adequate number of subjects needed for a safety database.

Sample size estimates were calculated for each of the co-primary efficacy endpoints, absolute change from baseline (CFB) in facial inflammatory lesion counts and facial IGA success (based on at least 2-point decrease from baseline in IGA score), and the **first** secondary efficacy endpoint, percent CFB in facial inflammatory lesion counts at Week 12 **using a last observation carried forward (LOCF) method of imputation**. The results from a recent study (Study PR-10411) of sarecycline compared to placebo treatment were used to estimate the sample size needed to show a significant difference between the treatments at $\alpha=0.05$ and 90% power using two-sided tests and a 1:1 randomization. It should be noted that one outlier in the data for Study PR-10411 was removed from the estimate for absolute CFB in inflammatory lesion counts in order to provide more accurate estimates for the sample size determination. Results of the calculations and the estimates used in the calculations are provided below:

Continuous Endpoints ¹	Sarecycline CFB or %CFB	Placebo CFB or %CFB	Common SD	Sample per Treatment	Total Sample Size
Absolute CFB in inflammatory lesion counts (co-primary)	16	13	12	338	676
Percent CFB in inflammatory lesion counts (secondary)	39%	52%	41%	210	420

¹ Sample size was based on a two sample t-test of no difference between the treatments.

Dichotomous Endpoints ¹	Sarecycline Rate	Placebo Rate	Difference in Rates	Sample per Treatment	Total Sample Size
IGA Success (2-point decrease in IGA score from baseline and a score of clear/almost clear; co-primary)	23%	10%	13%	170	340

¹ Sample size was based on a χ^2 test of no difference between the proportions.

While the IGA scale proposed for the Phase 3 studies is slightly different than the IGA scale in the Phase 2, the number of subjects to be enrolled (500 per treatment; 1000 total) should provide more than sufficient power for the efficacy evaluations. Additionally, a larger sample is needed in order to provide sufficient numbers of subjects on sarecycline treatment for a safety database.

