- Mixed model repeated measures (MMRM) analysis will be used to explore the sensitivity of data handling for CFB in inflammatory lesion counts for subjects who withdraw from the study. The model will include the fixed effects of treatment, pooled site, and visit, the baseline value as a covariate, and the treatment-by-visit interaction term. An unstructured covariance matrix will be used initially in the model for the correlation pattern among the repeated measures. If this does not converge, then the Toeplitz covariance structure (TYPE=TOEP in SAS MIXED procedure) will be used instead. If the results from the MMRM analyses differ qualitatively with the results from the primary efficacy analysis, further analyses will be performed to investigate the causes of the difference. However, the results from the primary efficacy analysis will be considered the primary efficacy results.
- A rank transformation will be applied to each of the multiple datasets created from the MI approach and the analysis will proceed for Week 12 using an ANCOVA model on the ranks with the baseline value as a covariate and effects of treatment and (pooled) site. Tied values will receive the mean value (midranks) of the corresponding ranks.

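### The MMRM check of the lesion-count co-primary fits one baseline slope to all four visits, and its fallback fits one variance, so a supportive analysis can mislead under specific conditions

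*Protocol*

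**What the plan says.** Lesion counts are taken at baseline and at four treatment visits: "IGA scores and lesion counts at baseline and following 3, 6, 9, and 12 weeks of treatment" (Protocol, Synopsis). Among the sensitivity analyses for continuous variables, Protocol 11.5.6 gives the MMRM for change from baseline (CFB) in inflammatory lesions: "The model will include the fixed effects of treatment, pooled site, and visit, the baseline value as the covariate, and the treatment-by-visit interaction term". SAP 10.1.1 has the same terms: "The model will include the fixed effects of treatment, pooled site, and visit, the baseline value as a covariate, and the treatment-by-visit interaction term". Treatment is crossed with visit. Baseline and pooled site are not.

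On covariance, Protocol 11.5.6 says "An unstructured covariance matrix will be used initially in the model for the correlation pattern among the repeated measures". It then says "If this does not converge, then the Toeplitz covariance structure (TYPE=TOEP in SAS MIXED procedure) will be used instead". The SAP repeats both steps. Neither document names a heterogeneous-variance alternative or robust standard errors.

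The stated purpose is to examine how the handling of withdrawals affects the result. If the MMRM differs qualitatively from the "primary efficacy analysis, further analyses will be performed to investigate the causes of the difference". Both documents add that the primary analysis remains the primary result.

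Elsewhere the plan lets the baseline slope be specific to the visit. The primary ANCOVA is fitted to Week 12 alone (Protocol 11.5.1, SAP 10.1.1). The secondary ANCOVAs are run separately for each visit (SAP 10.2). The multiple imputation works within arm and uses baseline together with all visits (Protocol 11.4.3, SAP 16.2).

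**The concern.** The slope of CFB on baseline often steepens over time, as counts become less correlated with baseline. A single slope is then a compromise across visits and need not fit Week 12. The part of the Week 12 baseline effect that it misses is absorbed elsewhere. If those still contributing at Week 12 have different baseline counts in the two arms, some of it is absorbed by the treatment contrast.

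Dropout that differs by arm is plausible here. Protocol 9.3.4 withdraws subjects who stop drug and requires withdrawal for clinically significant worsening of acne. However, only the part of dropout that is related to baseline severity feeds this bias.

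The MMRM is the only likelihood-based check listed for this endpoint; the others are per-protocol observed cases, LOCF, baseline carried forward and a rank analysis of the imputed data. Both the MMRM and the imputation rely on data being missing at random, so a gap between them should be informative about withdrawals. With a common slope, part of the gap can come from the model restriction instead.

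The fallback raises a separate issue. TYPE=TOEP has one variance for all visits, so the Week 12 contrast would borrow its variance from earlier visits.

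**Working it through.** **Inputs from the documents.** Protocol 11.1 gives a difference of 16 - 13 = 3 lesions, SD 12, 338 per arm, and 500 per arm to be enrolled, "at $\alpha=0.05$ and 90% power using two-sided tests and a 1:1 randomization".

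**The plan's own figure.** n per arm = 2(1.960 + 1.282)² × (12/3)² ≈ 337. The exact two-sample t calculation gives 337.2, rounded up to 338, as stated. The Week 12 SE with 500 per arm and full data is 12 × √(2/500) = 0.76 lesions.

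**Assumptions.** The documents give no visit-specific slopes, SDs, correlations or dropout rates. All those below are assumed. The bias and fallback simulations omit the site term.

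**1. Common slope, unstructured covariance.** Suppose the true mean at visit v contains b_v × baseline and the model fits a single b. At Week 12 the leftover is (b_12 - b) × baseline. Randomisation balances this between arms when data are complete or dropout is alike in both. It does not cancel when the arms lose subjects with different baselines.

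*Set A:* 200,000 subjects, true difference -3, SDs 8/10/11/12. The table shows the common-slope estimate minus the baseline-by-visit estimate at Week 12, at nominal 10% / 20% dropout.

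| Dropout mechanism | Slopes -0.20 to -0.50 | Slopes -0.10 to -0.60 |
|---|---|---|
| Completely random | -0.003 / -0.011 | -0.007 / 0.009 |
| Driven by prior response | 0.009 / 0.007 | 0.001 / 0.008 |
| Baseline-related, same in both arms | -0.008 / 0.007 | -0.032 / 0.036 |
| Baseline-related, opposite by arm | 0.165 / 0.357 | 0.308 / 0.667 |

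In the last row the baseline-by-visit fit was about 0.05 from the truth. The simulation error is 12 × √(2/100,000) = 0.05, so that is noise.

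*Set B:* no true effect, SDs 9/10.5/11.5/12, baseline SD about 7.3, about 14% missing at Week 12, and slopes running from -0.30 to -0.45, -0.20 to -0.50 or -0.10 to -0.65.
- Baseline-related dropout in placebo only: -0.07, -0.17, -0.29 (500 per arm, 1500 replicates). A separate fit with 150,000 per arm gave -0.06, -0.13, -0.21.
- Opposite patterns by arm: -0.12, -0.27, -0.46, and -0.13, -0.25, -0.43 in the large fit.
- Same pattern in both arms: under 0.01 (large fit).

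The material cases therefore run from 0.06 to 0.67 lesions: 0.06/3 = 2% and 0.67/3 = 22% of the planned difference. The sign is positive in Set A and negative in Set B. Swapping which arm has which dropout pattern reverses it.

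**2. Fallback.** With one variance, the ratio of the model SE to the true Week 12 SE is about √(mean of the four variances)/12, and coverage is 2Φ(1.96 × ratio) - 1. For example, SDs 10/11/11.5/12 give √((100 + 121 + 132.25 + 144)/4) = 11.15, and 11.15/12 = 0.929.

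| Assumed SDs, Weeks 3/6/9/12 | SE ratio | Coverage |
|---|---|---|
| 12/12/12/12 | 1.00 | 95.0% |
| 10/11/11.5/12 | 0.93 | 93.1% |
| 9/10/11/12 | 0.88 | 91.5% |
| 8/10/11/12 | 0.86 | 90.9% |
| 7/9/11/12 | 0.83 | 89.5% |
| 14/13/12.5/12 | 1.07 | 96.5% |

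A simulation with SDs 8/10/11/12 (1000 subjects, 15% nominal random dropout, 150 runs) gave a mean TOEP SE of 0.69 against an empirical SD of 0.79, with coverage of 92%. The unstructured fit gave 0.82 against 0.80, with coverage of 96%. The Monte Carlo error of coverage is about 2 points.

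**3. Does the interaction term align the MMRM with the ANCOVA?** Complete data were simulated with 40 pooled sites (assumed, 100 replicates, Set B SDs and slopes). The per-trial gap between MMRM and Week 12 ANCOVA had an SD of 0.13-0.27 lesions as planned. With baseline-by-visit added it was about 0.11 without true site effects, and 0.17-0.18 with a site-by-visit SD of 2. Mean gaps were about zero both ways. What remains comes from pooled site, which the MMRM does not cross with visit.

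**The case against.** The strongest reply is that this hardly matters. The MMRM is supportive, further work follows only from a qualitative difference, and the primary result stands regardless. Even the largest shift found, 0.67 lesions, is 0.67/0.76 = 0.88 of a Week 12 SE. At the planned effect, 500 per arm and full data, power is 97.7%. A shift of 0.46 against sarecycline leaves Φ((3 - 0.46)/0.759 - 1.96), about 92%; a shift of 0.67 leaves about 87%. A reversal is unlikely. The imputation also already conditions on baseline within arm, so the primary analysis handles this kind of dropout. All of that stands, and it sets the severity.

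A reader might infer more than the documents support:
- *That the Week 12 MMRM is biased as planned.* The constraint is always there; the bias is not. It needs both a slope that changes over visits and baseline-related dropout that differs by arm. The documents show neither.
- *That the bias favours sarecycline.* Its sign depends on which arm loses which subjects.
- *That the planned intervals are too narrow.* Under the unstructured matrix the model SE was adequate. Narrow intervals need both the fallback and rising variance. The matrix has 10 parameters for 4 visits and about 1000 subjects, so failure to converge is unlikely.
- *That the trial's type I error is inflated.* The reduced coverage belongs to a sensitivity model that carries no share of alpha.

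What survives is that the restriction is out of line with the rest of the plan, serves no stated purpose and is easily removed.

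**Conclusion.** Holds as a low-severity, optional refinement. Both documents fit one baseline slope to four visits in the MMRM. Where the slope changes over visits and baseline-related dropout differs by arm, the Week 12 estimate shifts by roughly 0.1 to 0.7 lesions in either direction (about 2-22% of the planned 3 lesions). Otherwise the shift is about 0.04 lesions or less. If TYPE=TOEP were ever used, the Week 12 SE would be about 0.83-0.93 of its proper size under the rising SDs assumed, and about 1.07 under the falling SDs.

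Every size rests on assumed slopes, SDs and dropout, since the documents supply only SD 12, the 3-lesion difference and the sample size. Only the reliability of one robustness check is affected; the co-primary conclusion is not.

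**What to change.** In Protocol 11.5.6 and SAP 10.1.1:
1. Add the baseline-by-visit interaction to the MMRM fixed effects. In the simulations this removed the bias to within simulation error.
2. Replace TYPE=TOEP with a fallback that keeps a separate variance for each visit, such as TYPE=TOEPH.

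The cost is three extra degrees of freedom, one model term and one keyword. It needs no new data and leaves the primary analysis unchanged. The text should not promise that the revised MMRM will reproduce the Week 12 ANCOVA with complete data, because pooled site is still a main effect not crossed with visit.
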